11.1. Adverse Events

An AE is any untoward medical occurrence in a subject or clinical study subject, temporally associated with the use of study intervention, whether or not considered related to the study intervention. An AE can therefore be any unfavorable and unintended sign (including an abnormal laboratory finding), symptom, or disease (new or exacerbated) temporally associated with the use of study intervention.

A treatment-emergent AE (TEAE) is defined as an AE that meets any of the following conditions:

- begins on or after the first dose of study drug and before the end of study drug + 30 days;
- begins before the first dose of study drug and worsens in severity on or after the first dose of study drug and before the end of study drug + 30 days;
- is completely missing an onset date and end date;
- is completely missing an onset date and the end date is on or after the first dose of study drug.

For the purpose of inclusion in TEAE tables, incomplete AE onset and end dates will be imputed as follows:

Missing onset dates (where UN and UNK indicate unknown or missing day and month respectively):

- UN-MMM-YYYY: If the month and year are different from the month and year of the first dose of study drug, assume 01-MMM-YYYY. If the month and year are the same as the first dose of study drug month and year, and the end date (after any imputation) is on or after the first dose of study drug, then assume the date of the first dose of study drug. If the month and year are the same as the first dose of study drug month and year, and the end date (after any imputation) is prior to the first dose of study drug, then assume the end date for the onset date.
- DD-UKN-YYYY/UN-UNK-YYYY: If the year is different from the year of first dose of study drug, assume 01-JAN-YYYY of the year the data was collected. If the year is the same as the first dose of study drug year, and the end date (after any imputation) is on or after the first dose of study drug, then assume the date of the first

dose of study drug. If the year is the same as the first dose of study drug, and the end date (after any imputation) is prior to the first dose of study drug, then assume the end date for the onset date.

Missing end dates (where UK and UNK indicate unknown or missing day and month respectively):

- UN-MMM-YYYY: Assume the last day of the month;
- DD-UNK-YYYY/UK-UNK-YYYY: Assume DD-DEC-YYYY or 31-DEC-YYYY respectively.

All adverse events will be classified by SOC and PT according to MedDRA (Version 21.0). Percentages will be calculated based on the number of subjects in the Safety Set, unless otherwise specified.

An overview summary of the number and percentage of subjects with any TEAE, serious TEAE, study drug-related TEAE, study drug-related serious TEAE, TEAE leading to study discontinuation/ early withdrawal, TEAE leading to treatment discontinuation, and AE leading to death will be provided by treatment group.

Summaries of the total number of TEAEs and the number and percentage of subjects with at least one TEAE will be provided by treatment group and overall. TEAEs will be presented in descending order of frequency by SOC. Likewise, within each SOC, the PTs will be presented by descending order of frequency.

11.1.1. Incidence of Adverse Events

Summaries of the number and percentage of subjects with at least one TEAE will be provided for each treatment group by SOC and PT. Subjects that report more than one event will only be counted once for each level of SOC and PT summary.

This summary will be presented in descending order of frequency by SOC. Likewise, within each SOC, the PTs will be presented by descending order of frequency.

All AEs will be presented in a listing on the Safety Set.

11.1.2. Severity of Adverse Event to Study Drug

A summary of TEAEs by severity will be presented in a table. The possible severities are 'Mild,' 'Moderate,' and 'Severe.' In this table, if a subject reported multiple occurrence of the same TEAE, only the most severe will be presented. Treatment-emergent AEs that are

missing severity will be presented in tables as ‘Severe’ but will be presented in the data listing with a missing severity.

This summary will be presented in descending order of frequency by SOC. Likewise, within each SOC, the PTs will be presented by descending order of frequency.

11.1.3. Relationship of Adverse Events to Study Drug

The investigator will provide an assessment of the relationship of the event to the study drug. The possible relationships are ‘Not Related’, and ‘Related’. If a subject reports multiple occurrence of the same TEAE and any of those are ‘Related’, the subject will be counted as ‘Related’ for that TEAE. Treatment-emergent AEs that are missing a relationship will be presented in the summary table as ‘Related’ but will be presented in the data listing with a missing relationship.

This summary will be presented in descending order of frequency by SOC. Likewise, within each SOC, the PTs will be presented by descending order of frequency.

The TEAE data will be categorized and presented by SOC, PT, and severity, for ‘Related’ and ‘Not Related’ separately.

11.1.4. Serious Adverse Events

The seriousness of an AE should be assessed by the Investigator independently from the severity of the AE. A serious AE (SAE) is defined as any untoward medical occurrence that at any dose results in death, is considered life-threatening, is a congenital anomaly/birth defect, requires in-subject hospitalization or prolongation of existing hospitalization, or results in significant disability.

A summary of the total number of treatment-emergent SAEs and the number and percentage of subjects with at least one treatment-emergent SAE will be provided for each treatment group and presented by SOC and PT in a manner similar to that described in [Section 11.1.1](#).

A summary of treatment-emergent SAEs by relationship to study drug will be presented in a table in a manner similar to that described in [Section 11.1.1](#).

All SAEs will be presented in a listing on the Safety Set.

11.1.5. Adverse Events Leading to Treatment Discontinuation

A summary of TEAEs which leading to study drug discontinuation, as reported in Adverse Events CRF page (where action taken with study treatment will be “Drug Permanently

Withdrawn") will be presented in a table. Subjects that report more than one event will only be counted once for each level of SOC and PT summary.

This summary will be presented by SOC, PT in a manner similar to that described in [Section 11.1.1](#).

All AEs leading to treatment discontinuation will be presented in a listing on the Safety Set.

11.1.6. Adverse Events Leading to Study Discontinuation

A summary of TEAEs leading to study discontinuation, as reported in 'Study Completion/Termination' CRF page (early withdrawals where primary reason for termination is 'Adverse Event'), will be presented in a table. Subjects that report more than one event will only be counted once for each level of SOC and PT summarisation.

This summary will be presented by SOC, PT in a manner similar to that described in [Section 11.1.1](#).

All AEs leading to study discontinuation will be presented in a listing on the Safety Set.

11.1.7. Overdose

The anticipated pattern of events or symptoms following intentional or accidental overdose with safinamide is that related to its pharmacodynamic profile (MAO-B inhibition with activity dependent inhibition of sodium channels). The symptoms of excessive MAO-B inhibition (increase in dopamine level) could include hypertension, postural hypotension, hallucinations, agitation, nausea, vomiting and dyskinesia.

If the investigator identifies a subject has taken an accidental overdose but none of the symptoms of overdose were reported, then the accidental overdose will not be recorded as an AE. If the investigator identifies an intentional overdose with suicidal intent, then this will be recorded as an SAE.

The number and percentage of subjects with any overdose will be displayed, as reported on the "Drug Accountability" eCRF page.

A listing will be provided for intentional overdose events. Intentional overdose will be reported as AE/SAE and will be identified based on MedDRA codes.

The listing will be based on the Safety Set.

11.1.8. Death

All subjects who have an AE with an outcome of ‘Death’ will be presented in a listing using the Safety Set.

11.2. Telephone Contact

All data will be presented in a listing on the Safety Set.

11.3. Clinical Laboratory Evaluations

Summary tables presenting numbers and percentages at Screening and Week 16 visits will be presented for clinical laboratory tests, by treatment group for subjects in the Safety Set. The following laboratory test results will be included: Normal; Abnormal (Clinically Significant), Abnormal (Not Clinically Significant).

All data will be presented in a listing on the Safety Set.

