1.2. Schema

1.3. Schedule of Activities (SoA)

For detailed description of assessments see Study Assessments and Procedures.

| Visit | 1 Screening | 2 Baseline * | 3 Interim Week 4 * | 4 Interim Week 8 * | 5 EoT Week 16 * | 6 Call | |
|-------------------------|------------------------------------|--------------------|-----------------------------|-----------------------------|--------------------------|-----------|---|
| Day / Procedure | (up to 14 days before Day 1) | 1 | 28 ± 3 | 56 ± 3 | 112 ± 3 | 119 ± 3 | Notes* |
| Informed consent | X | | | | | | After informed consent signing, enter details in IWRS to obtain screening number. |
| Eligibility criteria | X | X | | | | | Check prior to randomisation/ 1 st dose of study medication |
| Randomisation | | X | | | | | Use IWRS to randomise |
| Demographics | X | | | | | | Age, sex, ethnicity, smoking and alcohol use |
| Medical history | X | | | | | | PD diagnosis, Hoehn & Yahr staging, etc. |
| Vital signs | X | X | | | X | | Heart rate, systolic and diastolic blood pressure |

| Visit | 1 Screening | 2 Baseline * | 3 Interim Week 4 * | 4 Interim Week 8 * | 5 EoT Week 16 * | 6 Call | |
|--|------------------------------------|--------------------|-----------------------------|-----------------------------|--------------------------|-----------|--|
| Day / Procedure | (up to 14 days before Day 1) | 1 | 28 ± 3 | 56 ± 3 | 112 ± 3 | 119 ± 3 | Notes* |
| Physical examination and neurological examination | X | | | | X | | |
| MMSE | X | | | | | | |
| eDiary Issue, Training and return | X | X | | | X | | |
| eDiary Review | | X | X | X | X | | Participant to complete diary for 7 days prior to each visit. |
| NRS Review | | X | | | | | For eligibility: PI checks NRS score to confirm eligibility |
| MDS-UPDRS | | X | X | X | X | | |
| CGI-S | | X | X | X | X | | |
| CGI-C | | | X | X | X | | |
| PGI-C | | | X | X | X | | |
| HADS | | X | | | X | | |

| Visit | 1 Screening | 2 Baseline * | 3 Interim Week 4 * | 4 Interim Week 8 * | 5 EoT Week 16 * | 6 Call | |
|---|------------------------------------|--------------------|-----------------------------|-----------------------------|--------------------------|-----------|---|
| Day / Procedure | (up to 14 days before Day 1) | 1 | 28 ± 3 | 56 ± 3 | 112 ± 3 | 119 ± 3 | Notes* |
| Blood draw | X | | | | X | | For Haematology & Clinical chemistry |
| Pregnancy test | | X | | | X | | Urine dipstick test for WOCBP only |

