Following completion of 16 weeks' of treatment or in the event of premature discontinuation, the following End of Treatment (EOT) assessments and procedures should be performed.

- Neurological & Physical examination.
- Vital signs (heart rate, systolic and diastolic blood pressure measured after at least 5 minutes in the supine position).
- MDS-UPDRS (part IB and II), HADS and PGI-C completed by the participant.
- MDS-UPDRS (part IA, III and IV), CGI-S and CGI-C completed by the rater.
- Obtain blood sample for clinical laboratory assessments (haematology and clinical chemistry).
- Obtain urine sample only for WOCBP for urine (dipstick) pregnancy test.
- Record any changes or new concomitant medications and therapies.
- Record any AEs.
- Review and evaluate daily e-diary.
- Drug (all used & unused study medication) and final accountability.
- Collect e-diary.
- Agree on day & time for the follow up call in one weeks' time.

COVID- 19 outbreak: in order to ensure the continuity of the study, limiting the subjects' exposure to infection and overcoming travel restriction imposed by governments, a Contingency Plan has been finalized describing alternative procedures to be adopted in the study in order to mitigate the restriction and keeping participants in the trial (see Appendix 10 for details)

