Categorical data will be described using the subject count and percentage in each category. When counts are presented, in cases where the count is zero, the percentage will not be displayed in order to draw attention to the non-zero counts. A row denoted 'Missing' will be included in count tabulations where specified on the shells to account for missing values. The denominator for all percentages will be the number of populated subjects in that treatment within the analysis set of interest, unless otherwise specified. Frequency statistics will be displayed using one decimal place except for the display of 100% frequency which will be displayed as 'XX (100)'.

P-values will be rounded to three decimal places. If a p-value is less than 0.001 it will be reported as '<0.001'. If a p-value is greater than 0.999 it will be reported as '>0.999'. Confidence intervals will be displayed to one level of precision greater than the data

collected. Data will be displayed in all listings sorted by treatment group, country, centre, and subject ID.

Unless otherwise specified, baseline will be defined as the last non-missing evaluation prior to or on the date that the first dose of treatment is taken. Study day is defined in relation to the date of first dose of study drug. Therefore, when an assessment date is before the first dose:

Study day = assessment date - first dose date of study drug

and when an assessment is on or after the first dose:

Study day = assessment date - first dose date of study drug + 1

All analyses will be conducted using SAS Version 9.4 or higher and all data will be summarised based on the visit name collected on the eCRF page.

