The primary analysis of the primary efficacy variable will be based on the FAS data set. A secondary analysis of the primary efficacy parameter will be based on the PP set.

All other secondary efficacy analyses will be based on the FAS.

Safety analyses will be based on the safety analysis (SA) set.

5. Visit Attendance

The number and percentage of subjects who attended a visit or received a safety call will be presented for the following visits:

- Visit 2 (Baseline or Day 1)
- Visit 3 (Day 28)
- Visit 4 (Day 56)
- Visit 5 (EoT or Day 112)
- Follow-up Call

For Subjects with on-going site visits, wherever possible all efforts will be made to have the patient attend the hospital for their on-site study visits accordingly to schedule in the protocol. Assessment will be performed via phone call for Adverse event, Concomitant medication and e-questionnaires MDS-UPDRS, CGI-s and CGI-c if site visit is not possible. Anticipated data which will be missing due to COVID-19 outbreak is mostly LAB and ECG which requires on-site attendance.

6. Subject Disposition

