11.4. Vital Sign Measurements

A summary table presenting observed values of vital signs data at Screening, Baseline and Week 16 visits, and changes from baseline for Week 16 visit assessed in the supine position,

including systolic blood pressure (mmHg), diastolic blood pressure (mmHg), and heart rate (bpm), by treatment group for subjects in the Safety Set.

All vital sign data will be presented in a listing on the Safety Set.

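### The SAP 11.3 laboratory tables count each visit separately and do not pair a patient's results, so shifts short of clinical relevance have no by-arm summary; the Week 16 denominator is also unstated

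*SAP*

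**What the plan says.** SAP 11.3: "Summary tables presenting numbers and percentages at Screening and Week 16 visits will be presented for clinical laboratory tests", by treatment group on the Safety Set. The categories are "Normal; Abnormal (Clinically Significant), Abnormal (Not Clinically Significant"). No shift table, change from Screening or numeric summary is named. The section ends with "All data will be presented in a listing on the Safety Set".

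The Schedule of Activities (Protocol 1.3; SAP 14.1) has blood drawn only at Screening and at end of treatment/Week 16. The end-of-treatment procedures, blood sampling included, also apply to early leavers (Protocol section 8, Visit 5): "or in the event of premature discontinuation, the following End of Treatment (EOT) assessments and procedures should be performed".

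On missing data, SAP 5 says: "Anticipated data which will be missing due to COVID-19 outbreak is mostly LAB and ECG which requires on-site attendance". It gives no proportion and names no visit. The general rule on percentages, in SAP 4, is: "The denominator for all percentages will be the number of populated subjects in that treatment within the analysis set of interest", unless otherwise specified. A row for missing values appears only where the table shells call for one, and the shells are not part of the documents.

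Vital signs, by contrast, get a within-patient summary in SAP 11.4: "changes from baseline for Week 16 visit assessed in the supine position".

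**The concern.** Safety and tolerability is a stated secondary objective, and Screening with Week 16 is the whole scheduled laboratory record. The useful question is how many patients in each arm who were normal at Screening became abnormal on treatment, or moved from abnormal NCS to abnormal CS. Two separate columns of counts do not answer it, because the Week 16 count mixes carried-over abnormalities with new ones, and resolved abnormalities offset new ones.

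A second, separable matter is the denominator. If some patients have a Screening sample and no later one, the Week 16 percentage depends on whether it is taken over patients tested or over all patients in the set. SAP 11.3 does not say which.

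**Working it through.** The plan states no figure on this point, so there is none to reproduce. The check asks what the planned tables can identify.

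**Inputs.** The planned 105 randomised 2:1 (Protocol 1.1) gives 105 × 2/3 = 70 safinamide and 105/3 = 35 placebo. The documents give neither abnormality rates nor the proportion of laboratory results missing. Both are assumed below: 10%, 20% and 30% abnormal; 0%, 20% and 40% missing at Week 16.

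**Formula.** Let N be tested at Screening, a abnormal at Screening, m tested at Week 16 (all of them also tested at Screening), and b abnormal at Week 16, with CS and NCS combined. The number newly abnormal lies between

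- lower = max(0, b − min(a, m))
- upper = min(b, m − max(0, a − (N − m)))

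Example, no missing samples, 20% abnormal, safinamide: lower = max(0, 14 − 14) = 0; upper = min(14, 70 − 14) = 14.

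| Assumed abnormal | Assumed missing at Week 16 | Safinamide: Screening; Week 16; new | Placebo: Screening; Week 16; new |
|---|---|---|---|
| 10% | 0% | 7/70; 7/70; 0 to 7 | 4/35; 4/35; 0 to 4 |
| 20% | 0% | 14/70; 14/70; 0 to 14 | 7/35; 7/35; 0 to 7 |
| 30% | 0% | 21/70; 21/70; 0 to 21 | 10/35; 10/35; 0 to 10 |
| 20% | 20% | 14/70; 11/56; 0 to 11 | 7/35; 6/28; 0 to 6 |
| 20% | 40% | 14/70; 8/42; 0 to 8 | 7/35; 4/21; 0 to 4 |

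In every row the tables allow none of the Week 16 abnormalities to be new, or all of them. In the 20%, no-missing row the two arms look identical, yet the difference in new abnormalities (safinamide minus placebo) could be anywhere from 0/70 − 7/35 = −20 percentage points to 14/70 − 0/35 = +20 points. The gap therefore exists with complete data and does not depend on COVID-19.

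**Denominator.** With 40% missing on safinamide, 8 abnormal is 8/42 = 19.0% of those tested but 8/70 = 11.4% of the arm, against 14/70 = 20.0% at Screening. With 20% missing, 11 abnormal is 11/56 = 19.6% or 11/70 = 15.7%. The distortion arises only if the rule in SAP 4 means everyone in the set. If it means those with data, there is none.

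**Other routes in the plan.**

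- The SAP 11.3 listing shows each patient's results, so new abnormalities can be found by hand where both samples exist.
- Protocol 8.2.4 sends clinically relevant laboratory changes to the adverse event page. SAP 11.1 treats abnormal laboratory findings as possible adverse events, defines treatment emergence by onset or worsening after first dose, and 11.1.1 tabulates these events by arm.
- A change from normal to abnormal NCS that the investigator does not consider clinically relevant reaches neither an adverse event table nor any other by-arm summary. It appears only in the listing.

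**The case against.** The strongest reply is that the important cases are already covered. Clinically relevant changes become adverse events and are summarised by arm as treatment-emergent; possible severe liver injury must be reported as serious (Protocol Appendix 2); and the listing covers about 105 patients. This stands. A reader might infer from 11.3 alone that new abnormalities cannot be told from old ones at all. The documents do not support that: it is true of the summary tables, not of the plan. What remains is that a listing is not a by-arm summary, and that the adverse event route depends on investigator judgement.

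A reader might also infer from SAP 5 that Week 16 samples will largely be lost and that a false fall in abnormalities will follow. That too goes beyond the text. SAP 5 describes which kinds of data will be missing, not how much, and does not name Week 16, although Week 16 is the only scheduled draw after Screening. The contingency plan (Protocol Appendix 10) allows samples at an alternative location's local laboratory and visits outside the window, and early leavers are due end-of-treatment bloods. The false fall further requires one reading of an ambiguous denominator rule, and the shells may settle it.

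Two more points have some force. Physical and neurological examinations (SAP 11.5, 11.6) use the same two-visit counts, so the SAP is consistent in how it handles categorical safety data; vital signs are numeric and lend themselves to a change score. And randomisation keeps the Week 16 comparison between arms meaningful. That comparison, however, shows new minus resolved abnormalities, not new ones.

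Finally, replacing the visit counts with shift tables would hide patients who have only one sample. That is right, and the fix adds to the counts instead.

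**Conclusion.** The point holds as a gap in safety reporting. The SAP 11.3 tables do not pair results, so they cannot show how many patients became abnormal on treatment; at an assumed 20% abnormal at both visits with nothing missing, they fit 0 to 14 of 70 on safinamide and 0 to 7 of 35 on placebo. The listing and, for clinically relevant changes, the adverse event tables fill part of the gap. Shifts from normal to abnormal NCS have no by-arm summary.

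Separately, 11.3 does not say that Week 16 percentages are taken over patients tested, although SAP 5 expects laboratory data to be among the main losses to COVID-19. Its effect cannot be sized from the documents: the 19.0% against 11.4% example rests on an assumed 40% missing and on one reading of SAP 4.

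This is a low-priority, inexpensive improvement. Safety is planned as descriptive, and the efficacy analyses are unaffected.

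**What to change.** Before database lock, amend SAP 11.3 and its shells as follows.

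1. Keep the Screening and Week 16 counts by arm, state that percentages use the number tested at that visit, and include a missing row.
2. Add, by arm and test, a 3 × 3 shift table of Screening category by Week 16 (or early termination) category among patients with both results, and show the number with no post-baseline result.
3. State whether early termination samples are shown under Week 16. At present 11.3 is silent, and SAP 4 summarises by the visit name on the eCRF page.

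The categories are already collected, so the cost is shells and programming. The downsides are volume and sparseness: SAP 11.3.1 lists 15 haematology tests and 11.3.2 lists 13 chemistry tests, 28 in all, and with 35 placebo patients planned many cells will be small or empty. Patients without a paired result fall out of the shift percentages, which is why the visit counts and the number without a post-baseline result need to stay beside them.

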7.3. Lost to Follow Up

A participant will be considered lost to follow-up if he or she repeatedly fails to return for scheduled visits and is unable to be contacted by the study site.

The following actions must be taken if a participant fails to return to the clinic for a required study visit:

- The site must attempt to contact the participant and reschedule the missed visit as soon as possible and counsel the participant on the importance of maintaining the assigned visit schedule and ascertain whether or not the participant wishes to and/or should continue in the study.

- Before a participant is deemed lost to follow up, the investigator or designee must make every effort to regain contact with the participant (where possible, 3 telephone calls and, if necessary, a certified letter to the participant's last known mailing address or local equivalent methods). These contact attempts should be documented in the participant's medical record.

8. Study Assessments and Procedures

- Study procedures and their timing are summarized in the SoA. Protocol waivers or exemptions are not allowed.
- Immediate safety concerns should be discussed with the sponsor immediately upon occurrence or awareness to determine if the participant should continue or discontinue study intervention.
- Adherence to the study design requirements, including those specified in the SoA, is essential and required for study conduct.
- All screening evaluations must be completed and reviewed to confirm that potential participants meet all eligibility criteria. The investigator will maintain a screening log to record details of all participants screened and to confirm eligibility or record reasons for screening failure, as applicable.
- Procedures conducted as part of the participant's routine clinical management and obtained before signing of the ICF may be utilized for screening or baseline purposes provided the procedures met the protocol-specified criteria and were performed within the time frame defined in the SoA.
- The maximum amount of blood collected from each participant over the duration of the study, including any extra assessments that may be required, will not exceed 20 mL. Repeat or unscheduled samples may be taken for safety reasons or for technical issues with the samples.
- Local labs will be used in this study

Visit 1: Screening visit (7 to 14 days before Day1)

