10.2. Appendix 2: Clinical Laboratory Tests

- The tests detailed in Table 1 will be performed by the local laboratory.
- If the local laboratory results are used to make either a study intervention decision or response evaluation, the results must be entered into the eCRF.
- Protocol-specific requirements for inclusion or exclusion of participants are detailed in Section 5 of the protocol.
- Additional tests may be performed at any time during the study as determined necessary by the investigator or required by local regulations.
- Investigators must document their review of each laboratory safety report, by signing and dating it.

Table 1 Protocol-Required Safety Laboratory Assessments

| Laboratory Assessments | Parameters | | | |
|------------------------|---------------------------------|-----------|--|------------------------------|
| Hematology | Platelet Count | | White blood cell (WBC) count with Differential: Neutrophils Lymphocytes Monocytes Eosinophils Basophils | |
| | Red blood cell (RBC) Count | | | |
| | Hemoglobin | | | |
| | Hematocrit | | | |
| Clinical Chemistry | Blood urea nitrogen (BUN) | Potassium | Aspartate Aminotransferase (AST)/ Serum Glutamic-Oxaloacetic Transaminase (SGOT) | Total and direct bilirubin |
| | Creatinine | Sodium | Alanine Aminotransferase (ALT)/ Serum Glutamic-Pyruvic Transaminase (SGPT) | Total Protein |
| | | Calcium | Alkaline phosphatase | Gamma-glutamyltranspeptidase |
| Pregnancy Tests: | Dipstick - urine pregnancy test | | | |

NOTES :

¹ All events of ALT $\geq 3 \times$ upper limit of normal (ULN) and bilirubin $\geq 2 \times$ ULN ($>35\%$ direct bilirubin) or ALT $\geq 3 \times$ ULN and international normalized ratio (INR) >1.5 , if INR measured which may indicate severe liver injury (possible Hy's Law), must be reported as an SAE (excluding studies of hepatic impairment or cirrhosis).

10.3. Appendix 3: Adverse Events: Definitions and Procedures for Recording, Evaluating, Follow-up, and Reporting

Definition of AE

AE Definition

- An AE is any untoward medical occurrence in a patient or clinical study participant, temporally associated with the use of study intervention, whether or not considered related to the study intervention.
- NOTE: An AE can therefore be any unfavorable and unintended sign (including an abnormal laboratory finding), symptom, or disease (new or exacerbated) temporally associated with the use of study intervention.

Events Meeting the AE Definition

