11.3.2. Clinical Chemistry

The following laboratory tests will be included: Blood Urea Nitrogen (BUN), Potassium, Sodium, Creatinine, Calcium, Aspartate Aminotransferase (AST)/ Serum Glutamic-Oxaloacetic Transaminase (SGOT), Alanine Aminotransferase (ALT)/ Serum Glutamic-Pyruvic Transaminase (SGPT), Alkaline phosphatase, Total bilirubin, Direct bilirubin, Urea, Total Protein, and Gamma Glutamyl transpeptidase (GGT).

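### The laboratory tables in SAP 11.3 cannot show the protocol's own liver criterion and have no place for unscheduled on-treatment results

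*SAP*

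**What the plan says.** SAP 11.3 governs the laboratory output: "Summary tables presenting numbers and percentages at Screening and Week 16 visits will be presented for clinical laboratory tests", by treatment group on the Safety Set, using the three result categories. It adds that "All data will be presented in a listing on the Safety Set". It plans no numeric summary, change from baseline, shift table, worst on-treatment value or multiple of the upper limit of normal (ULN). SAP 11.3.2 names the liver tests as separate items, including AST, ALT and "Alkaline phosphatase, Total bilirubin, Direct bilirubin". SAP 4 (General Statistical Considerations) says that "all data will be summarised based on the visit name collected on the eCRF page".

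On the protocol side, note 1 to Table 1 in Appendix 2 sets a criterion with two branches:
- ALT at least 3 times ULN with bilirubin at least 2 times ULN and more than 35% direct bilirubin; or
- ALT at least 3 times ULN with INR above 1.5, if INR was measured.

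The note describes these as findings "which may indicate severe liver injury (possible Hy's Law), must be reported as an SAE". Protocol Section 8 allows extra blood samples: "Repeat or unscheduled samples may be taken for safety reasons or for technical issues with the samples".

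**The concern.** Safety and tolerability is a stated secondary objective, and the protocol has chosen a numeric threshold for possible severe liver injury. The laboratory tables cannot apply it. An ALT of 1.1 times ULN and one of 4 times ULN both count as abnormal and not clinically significant if the investigator so judges. A patient with raised ALT and raised bilirubin appears once under each test, just as two different patients with one abnormality each would.

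A rise found in an unscheduled sample during treatment that settles by Week 16 appears in the laboratory table only as a normal Week 16 result. At stake is whether a reader comparing arms could see a liver signal that is present in the collected data, without relying on each site having spotted and reported it.

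**Working it through.** No formula applies. The check sets the planned outputs beside the collection and reporting rules.

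**1. Scheduled samples.** The Schedule of Activities has blood draws at Screening and Visit 5 (Week 16) only. Under Visit 5 in Protocol Section 8, patients who stop early have the same end-of-treatment assessments. The two tabulated visits therefore cover every scheduled draw, and only one scheduled sample follows the first dose. SAP 5 expects laboratory data to be among the data most often lost to COVID-19.

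**2. Unscheduled samples.** Section 8 allows them, and Protocol 8.2.4 calls for repeats of clinically significant abnormal values. With summaries keyed to eCRF visit name (SAP 4) and two visits named (SAP 11.3), an unscheduled result has no column.

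**3. The criterion against the table.**

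| The Appendix 2 criterion needs | SAP 11.3 gives |
|---|---|
| Value as a multiple of ULN | Three categories without magnitude |
| ALT and bilirubin in the same patient | Each test counted separately |
| Direct bilirubin fraction | Direct bilirubin categorised on its own |
| INR, if measured | INR not in the SAP 11.3.2 list |

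**4. Other planned outputs.**

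| Situation | Laboratory tables | TEAE or SAE tables | Listing |
|---|---|---|---|
| Unscheduled on-treatment result, judged clinically relevant | No | Yes: 8.2.4 sends it to the AE page, and SAP 11.1.1 is not tied to visits | Yes |
| Unscheduled on-treatment result, not judged clinically relevant | No | No | Yes |
| Liver criterion met and reported | Separate categories only, at the two visits | Yes, if treatment-emergent, under the reported preferred term | Yes |
| Liver criterion met, not recognised | Separate categories only, at the two visits | Not as a liver-criterion event | Only as whatever values the database holds |

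Rows two and four are the gap.

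**5. Strength of the reporting route.** Appendix 2 makes every qualifying event an SAE. Appendix 3 makes an abnormal laboratory result an AE when the investigator considers it clinically significant, and says that what is not an AE cannot be an SAE. These passages need to be reconciled. The SAE definition in SAP 11.1.4 also omits the category of other medically important situations in Appendix 3, where a laboratory-only case without hospitalisation would most naturally fall. SAE tables are by system organ class and preferred term, so the reported term may not identify the case. Laboratories are local and there is no data monitoring committee.

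**6. Are the numbers in the database?** The documents do not settle this. Protocol 10.1.7 speaks generally of study data going to the eCRF or being transferred electronically, with laboratory data as its example. Appendix 2 explicitly requires eCRF entry of local results only when they inform an intervention decision or a response evaluation. The contingency plan asks for effort to collect normal ranges, but only for samples analysed at an alternative location.

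**The case against.** The strongest reply is that the plan already has a route for these events. Qualifying liver events are mandatory SAEs, and under SAP 11.1.4 "the number and percentage of subjects with at least one treatment-emergent SAE will be provided for each treatment group". Clinically relevant laboratory changes go to the AE page at any time. Investigators must document review of each laboratory report, source data are verified, and all laboratory data are listed. No scheduled time point is missed. This is a Phase IV trial of an approved drug that excludes moderate or severe liver failure, and neither document requires a table of ULN multiples.

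Most of this stands. A reader of SAP 11.3 might infer that liver cases and all unscheduled abnormalities vanish from the trial's tables. The documents do not support that: the omission is from the laboratory tables, and only unscheduled abnormalities not judged clinically relevant are confined to the listing. A reader might also want to size the problem with an upper confidence bound for zero observed cases. Such a bound depends only on the number of patients. It does not measure any harm from the table format, and the fix would not change it.

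What the reply does not answer is that every tabulated route starts with the investigator's recognition of the event. The listing holds data but neither compares arms nor checks that the criterion was applied. Numeric safety summaries are not foreign to this SAP: Section 11.4 gives observed values and changes from baseline for vital signs.

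**Conclusion.** The point holds in a limited form. The laboratory tables cannot show the Appendix 2 criterion and leave out unscheduled on-treatment results, and no planned output applies that criterion to the data by arm. Recognised and reported cases still reach the TEAE and SAE tables.

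The size cannot be expressed as a number from these documents, since it depends on how many qualifying or unscheduled results occur and go unreported. It is confined to the laboratory part of one secondary objective, and efficacy analyses are unaffected. It is a cheap improvement rather than a flaw that undermines the trial.

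The finding about the tables rests on reading SAP 4 and 11.3 as written. The full fix further assumes that numeric results and local ULNs are held, which the documents leave open.

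**What to change.** 1. In SAP 11.3, add to the existing category table a column for the worst result after the first dose, including unscheduled samples, by arm on the Safety Set. This needs only the categories already used, for whichever unscheduled results were entered.
2. Where numeric values and local ULNs are held, add a by-arm table of each patient's maximum post-first-dose ALT, AST and total bilirubin as multiples of ULN. Include a row applying the Appendix 2 criterion exactly as written, with the direct bilirubin condition and the ALT/INR branch where INR was measured. Show patients without ranges as not evaluable.
3. Before database lock, reconcile patients who meet that criterion with the SAE records.
4. If numeric values or ranges are not in the database, say so in the SAP, and state that item 1, the SAE and TEAE tables and the listing serve instead.

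The cost is SAP wording, one extra column, one extra table and a reconciliation step. Local-laboratory limits must be standardised, and some patients may not be evaluable. The change concerns analysis and reporting only and proposes no clinical rule.
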